## **Interim Analysis**

An interim analysis will be performed when half of subjects are enrolled to assess the safety and efficacy of the study.

### **7.3 Subject Population(s) for Analysis**

Analysis of the protocol-compliant population will be conducted. 3, 6, and 12 month evaluability will be assessed based upon the severity of the glioma disease process associated with brain tumor-related focal seizures and risk of imminent death from high-grade malignant primary brain tumor.

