Study Product, Dose, Route, Regimen	PER is a noncompetitive AMPA glutamate receptor antagonist. The two phases of the treatment portion of this study include a titration phase and a stable dosing phase. This study will have two treatment arms consisting of PER and alternative ASD arm. The PER arm will begin a titration phase with 2mg PER PO q.d. (may be split to b.i.d.) for one week and increase by 2mg/week until reaching an initial dose of 4mg PO q.d. (q.d. or b.i.d. dosing) is reached. Flexible dosing of PER above 4mg to a maximum of 8 mg daily will be compared to use of alternative ASDs and be guided by best clinical practices with dosing and indication within U.S. FDA guidelines.
Duration of Administration	Participants will be assigned to receive open label PER or an alternate ASD for at least 12 week and up to 40weeks for the remainder of the study. This includes 2-4 weeks of titration and up to 40 weeks of stable dosing. Reduction by 2 mg will be allowed in cases of efficacy if doses greater than 4 mg daily result in non-idiopathic side-effects.
Reference therapy	All comparisons will use standard ASDs as the reference therapy using an intent to treat study design for patients initiating or tapering off PER therapy.
Statistical Methodology	Statistical analysis will include Student T-test, Chi-square for categorical differences. An interim analysis will be performed when half of the targeted subjects are enrolled.

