### **3.4 Primary Endpoints**

- A. The number of patients with a high-grade glioma who achieve a > 50% reduction in focal seizures with PER 4 mg daily after failing 1 or more ASDs at 3 and 6 months.
  1. The overall survival of patients with high-grade glioma treated with PER at 3 months.
  2. Decline in neuropsychological function at 6 months.

All comparisons will use intent to treat model for patients initiated or exiting PER therapy. In event of patients not surviving till 12 months, most recent data prior to death will be used for correlation.

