### 5.3 Method for Assigning Subjects to Treatment Groups

Participants will be assigned to receive:

Group A: open label arm of adjunctive PER (study drug) for patients with seizures treated with at least 1 ASD administered in escalating divided doses of 2 mg/week to 4 mg daily with flexible dosing to 8 mg/day by 4 weeks. Subjects must undergo forced titration of 2 mg/week and be able to tolerate 4 mg to continue in the study. Concomitant ASD will be utilized according to best clinical practice.

or

Group B: continued open label treatment for patients with seizures treated with at least 1 ASD, as per best medical practice, without the use of PER.

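### The plan promises intent-to-treat for all comparisons, but 7.3 names only an undefined protocol-compliant set with severity-based evaluability, and nothing says which set is primary

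*Combined protocol and SAP*

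**What the plan says.** Two places commit the study to intent-to-treat. The Reference therapy row of the Study Summary applies to all comparisons an "intent to treat study design for patients initiating or tapering off PER therapy". Section 3.4 repeats it: "All comparisons will use intent to treat model for patients initiated or exiting PER therapy". Section 3.4 then adds a rule for deaths: "In event of patients not surviving till 12 months, most recent data prior to death will be used for correlation".

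Section 7.3 is the only section on analysis populations. It says "Analysis of the protocol-compliant population will be conducted", followed by "3, 6, and 12 month evaluability will be assessed based upon the severity of the glioma disease process", and it adds imminent risk of death as a second basis for evaluability. It does not define protocol compliance, give criteria for evaluability or mention intent-to-treat. Section 7.2 names no analysis set for any hypothesis.

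Three other places bear on the point:

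- The responder endpoint in 3.4 is a count without a denominator: "The number of patients with a high-grade glioma who achieve a > 50% reduction in focal seizures with PER 4 mg daily", assessed at 3 and 6 months.
- Section 5.3 sets a condition for Group A: "Subjects must undergo forced titration of 2 mg/week and be able to tolerate 4 mg to continue in the study". Group B has no matching tolerance condition; its defining feature is treatment "without the use of PER".
- Section 4.3 plans 10 subjects per group and leaves the choice of group to the treating physician.

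**The concern.** Two analysts could both follow the document and report different responder rates. One would divide by everyone enrolled in the group, the other by whoever is judged compliant and evaluable. The second denominator is fixed after enrolment, using information that can change after baseline.

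Glioma severity and closeness to death are also not neutral grounds for evaluability. Survival at 3 months and neuropsychological decline at 6 months are listed in 3.4, and MRI progression and neurocognitive change are secondary objectives in section 2. A set built on severity would be selected on information related to those same outcomes.

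The pilot exists to judge whether a larger trial is supported (7.1), and 7.2 attaches a 0.05 threshold to the seizure comparison. A response rate with no fixed denominator is a weak basis for that judgement.

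**Working it through.** **Plan's own figures.** The only arithmetic to reproduce is 10 + 10 = 20 subjects (4.3, 3.2), which agrees. Section 7.1 gives no effect size, response rate, dropout rate or power, so no stated figure depends on the analysis set.

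**Sections side by side.**

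| Question | Study Summary and 3.4 | 7.3 |
|---|---|---|
| Named set | Intent-to-treat | Protocol-compliant |
| Defined? | No; wording refers to patients starting or leaving PER | No |
| Subject who leaves PER | Covered by the intent-to-treat wording | Not stated |
| Subject who dies or is very ill | Last data before death used, for correlation | Evaluability judged on severity and imminent risk of death |
| Primary or supportive? | Not stated | Not stated |

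**Rates on assumed counts.** The group size of 10 is from 4.3. The numbers of responders and of subjects dropped are assumptions. Rate = responders retained / subjects retained.

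- All PER subjects kept: 3/10 = 30%.
- Three non-responders dropped: 3/(10 − 3) = 3/7 = 43%.
- Three dropped, one of them a responder: (3 − 1)/(10 − 3) = 2/7 = 29%.

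Now let both groups have a rate of 3/10. If three non-responders leave the PER group only, the difference is 3/7 − 3/10 = 0.129, about 13 points where there was none. If three non-responders leave each group, it is 3/7 − 3/7 = 0. In this illustration the bias comes from unequal loss. Section 5.3 makes unequal loss possible because the tolerance condition applies to Group A only.

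**P-values, if responders were compared between groups.** Section 7.2 names chi-square for categorical differences but does not spell out this test or its version. With a and b the responders and non-responders in the PER group, c and d those in Group B, and N = a + b + c + d:

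chi-square = N(ad − bc)² / [(a+b)(c+d)(a+c)(b+d)], 1 df.

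Example, 3/7 v 3/10: 17 × (3×7 − 4×3)² / (7 × 10 × 6 × 11) = 17 × 81 / 4620 = 0.298, P = 0.585.

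Two-sided P, uncorrected / Yates / Fisher, when only PER non-responders are dropped:

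| All enrolled | P | After dropping | P |
|---|---|---|---|
| 3/10 v 3/10 | 1.000 / 1.000 / 1.000 | 3/7 v 3/10 | 0.585 / 0.976 / 0.644 |
| 3/10 v 1/10 | 0.264 / 0.576 / 0.582 | 3/7 v 1/10 | 0.116 / 0.322 / 0.250 |
| 4/10 v 1/10 | 0.121 / 0.302 / 0.303 | 4/7 v 1/10 | 0.036 / 0.119 / 0.101 |
| 5/10 v 1/10 | 0.051 / 0.143 / 0.141 | 5/9 v 1/10 | 0.033 / 0.101 / 0.057 |
| 5/10 v 1/10 | 0.051 / 0.143 / 0.141 | 5/7 v 1/10 | 0.009 / 0.036 / 0.035 |

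The first two rows cross 0.05 in no version. The third and fourth cross only without correction, with smallest expected counts of 2.1 to 3.0. The last crosses in all three. Every crossing starts from an assumed gap of 30 or 40 points.

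**The case against.** The strongest reply is that there is no flat contradiction. Section 7.3 says a protocol-compliant analysis will be done; it does not say that it is the only one, the primary one, or a replacement for intent-to-treat. Intent-to-treat could govern the comparisons, with the compliant set as an extra analysis. That is correct, and a reader who infers that 7.3 withdraws the intent-to-treat commitment goes further than the text. What stands is that neither set is defined and no ranking is given.

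A reader might also infer that 7.3 excludes the sickest patients. It contains no exclusion rule. The sentence may only mean judging whether a very ill patient can be assessed at a visit, and the rule in 3.4 on data before death points towards keeping such patients. That rule is limited to correlation, however, and 7.3 does not refer to it, so the risk remains open.

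Unequal loss is likewise a possibility. The tolerance condition bears on Group A, but starting PER would depart from Group B's regimen, and severity could remove subjects from either group. Nothing fixes the direction.

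Finally, 7.2 describes a before-and-after comparison of seizure frequency and descriptive statistics for responders, so the between-group test above is a construction. The study is also unpowered (7.1) and not randomised (4.3). These points limit the consequence but do not supply the missing primary set.

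**Conclusion.** The concern holds as a gap in the plan: two analysis sets, neither defined, with no statement of which carries the main result. If 7.3 is used for the main result, subjects may be selected on post-baseline, outcome-related information, which sits badly with the treatment of deaths in 3.4.

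On assumed counts, the choice of set moves a 30% PER response rate to between 29% and 43%. The direction depends on who leaves and on whether loss is equal between groups. It would be tempting to conclude that the plan produces false significance for PER. The documents do not support that: the test is not specified, the counts are assumed, and the case with equal underlying rates gives P = 0.585.

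The effect is on how the pilot rate is read when a larger trial is considered. Analysis by assigned group prevents exclusions after assignment; it does not remove confounding by indication. This should be fixed, but it does not undermine the study.

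**What to change.** In 7.3:

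- Make the primary efficacy set all enrolled subjects in both groups, analysed by assigned group, with that number as the responder denominator. This also settles Group B's coverage.
- Define the protocol-compliant set by the same criteria in both groups, and use it only as a sensitivity analysis.
- Do not use glioma severity or risk of imminent death to exclude anyone from the primary set. Record an assessment that cannot be done as missing, with the reason, as 9.3 already requires.
- Report exits, deaths and missing assessments by group.
- State in advance one handling of exits and deaths for the responder endpoint, the same in both groups and consistent with 3.4, with a sensitivity analysis on observed data.

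Reconcile the Study Summary, 3.4, 5.3 and 7.3 on whether subjects who leave PER remain in the analysis. This concerns the analysis only and changes no clinical rule. Settle it before any results are examined, including the interim analysis in 7.2.

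The cost is protocol wording and a little more analysis work. The PER response rate may look less favourable than in a compliant-only set.

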## 8 Safety and Adverse Events

### 8.1 Definitions

#### Unanticipated Problems Involving Risk to Subjects or Others (UPIRTSO)

Any unanticipated problem or adverse event that meets the following three criteria:

- Serious: Serious problems or events that results in significant harm, (which may be physical, psychological, financial, social, economic, or legal) or increased risk for the subject or others (including individuals who are not research subjects). These include: (1) death; (2) life threatening adverse experience; (3) hospitalization - inpatient, new, or prolonged; (4) disability/incapacity - persistent or significant; (5) birth defect/anomaly; (6) breach of confidentiality and (7) other problems, events, or new information (i.e. publications, DSMB reports, interim findings, product labeling change) that in the opinion of the local investigator may adversely affect the rights, safety, or welfare of the subjects or others, or substantially compromise the research data, **AND**
- Unanticipated: (i.e. unexpected) problems or events are those that are not already described as potential risks in the protocol, consent document, not listed in the Investigator's Brochure, or not part of an underlying disease. A problem or event is "unanticipated" when it was unforeseeable at the time of its occurrence. A problem or event is "unanticipated" when it occurs at an increased frequency or at an increased severity than expected, **AND**
- Related: A problem or event is "related" if it is possibly related to the research procedures.

#### Adverse Event

An untoward or undesirable experience associated with the use of a medical product (i.e. drug, device, biologic) in a patient or research subject.

#### Serious Adverse Event

Adverse events are classified as serious or non-serious. Serious problems/events can be well defined and include;

- death
- life threatening adverse experience
- hospitalization
- inpatient, new, or prolonged; disability/incapacity
- persistent or significant disability or incapacity
- birth defect/anomaly

and/or per protocol may be problems/events that in the opinion of the sponsor-investigator may have adversely affected the rights, safety, or welfare of the subjects or others, or substantially compromised the research data.

All adverse events that do not meet any of the criteria for serious, should be regarded as **non-serious adverse events**.

#### Adverse Event Reporting Period

For this study, the study treatment follow-up period is defined as 12 months following the last administration of study treatment.

### **Preexisting Condition**

A preexisting condition is one that is present at the start of the study. A preexisting condition should be recorded as an adverse event if the frequency, intensity, or the character of the condition worsens during the study period.

### **General Physical Examination Findings**

At screening, any clinically significant abnormality should be recorded as a preexisting condition. At the end of the study, any new clinically significant findings/abnormalities that meet the definition of an adverse event must also be recorded and documented as an adverse event.

### **Post-study Adverse Event**

All unresolved adverse events should be followed by the sponsor-investigator until the events are resolved, the subject is lost to follow-up, or the adverse event is otherwise explained. At the last scheduled visit, the sponsor-investigator should instruct each subject to report, to the sponsor-investigator, any subsequent event(s) that the subject, or the subject's personal physician, believes might reasonably be related to participation in this study.

### **Abnormal Laboratory Values**

A clinical laboratory abnormality will be documented as an adverse event if the conditions of the laboratory are identified as outside the normal expected range for the parameter and in the investigators opinion requires an intervention (e.g., repeat testing, consequences on the disease state, exhibit evidence of organ toxicity, or necessitate dosage reduction, discontinuation of study drug, or additional follow-up).

### **Hospitalization, Prolonged Hospitalization or Surgery**

Any adverse event that results in hospitalization or prolonged hospitalization should be documented and reported as a serious adverse event unless specifically instructed otherwise in this protocol. Any condition responsible for surgery should be documented as an adverse event if the condition meets the criteria for an adverse event.

Neither the condition, hospitalization, prolonged hospitalization, nor surgery are reported as an adverse event in the following circumstances:

- Hospitalization or prolonged hospitalization for diagnostic or elective surgical procedures for a preexisting condition. Surgery should **not** be reported as an outcome of an adverse event if the purpose of the surgery was elective or diagnostic and the outcome was uneventful.
- Hospitalization or prolonged hospitalization required to allow efficacy measurement for the study.
- Hospitalization or prolonged hospitalization for therapy of the target disease of the study, unless it is a worsening or increase in frequency of hospital admissions as judged by the clinical investigator.

## **8.2 Recording of Adverse Events**

At each contact with the subject, the study team must seek information on adverse events by specific questioning and, as appropriate, by examination. Information on all adverse events should be recorded immediately in the source document, also in the appropriate adverse event section of the case report form (CRF). All clearly related signs, symptoms, and abnormal diagnostic, laboratory or procedure results should be recorded in the source document.

All adverse events occurring during the study period must be recorded. The clinical course of each event should be followed until resolution, stabilization, or until it has been ultimately determined that the study treatment or participation is not the probable cause. Serious adverse events that are still ongoing at the end of the study period must be followed up, to determine the final outcome. Any serious adverse event that occurs during the Adverse Event Reporting Period and is considered to be at least possibly related to the study treatment or study participation should be recorded and reported immediately.

## **8.3 Reporting of Serious Adverse Events and Unanticipated Problems**

When an adverse event has been identified, the study team will take appropriate action necessary to protect the study participant and then complete the Study Adverse Event Worksheet and log. The sponsor-investigator will evaluate the event and determine the necessary follow-up and reporting required.

### **8.3.1 Sponsor-Investigator reporting: notifying the Mayo IRB**

The sponsor-investigator will report to the Mayo IRB any UPIRTSOs and Non-UPIRTSOs according to the Mayo IRB Policy and Procedures.

### **8.3.2 Sponsor-Investigator reporting: Notifying the FDA**

The sponsor-investigator will report to the sponsor and the FDA all unexpected, serious suspected adverse reactions according to the required IND Safety Reporting timelines, formats and requirements.

Unexpected fatal or life threatening suspected adverse reactions where there is evidence to suggest a causal relationship between the study drug/placebo and the adverse event, will be reported as a serious suspected adverse reaction. This will be reported to the FDA on FDA Form 3500A, no later than 7 calendar days after the sponsor-investigator's initial receipt of the information about the event.

Other unexpected serious suspected adverse reactions where there is evidence to suggest a causal relationship between the study drug/placebo and the adverse event, will be reported as a serious suspected adverse reaction. This will be reported to the FDA on FDA Form 3500A, no later than 15 calendar days after the sponsor-investigator's initial receipt of the information about the event.

Any clinically important increase in the rate of serious suspected adverse reactions over those listed in the protocol or product insert will be reported as a serious suspected adverse reaction.

This will be reported to the FDA on FDA Form 3500A no later than 15 calendar days after the sponsor-investigator's initial receipt of the information about the event.

Findings from other studies in human or animals that suggest a significant risk in humans exposed to the drug will be reported. This will be reported to the FDA on FDA Form 3500A, no later than 15 calendar days after the sponsor-investigators initial receipt of the information about the event.

#### **8.4 Stopping Rules**

The Principal and Co-Investigators as well as Study Coordinator are responsible for individual safety monitoring. Stopping or interruption of the study may be necessary if a significant number of study participants develop unexpected clinical flaring or significant worsening, as judged by the principal investigator, study coordinator or sponsor, appears temporally linked with Perampanel administration to be used for the indication outlined in this protocol.

The Principal Investigator and/or Investigators will review all adverse event reports to determine if specific reports need to be made to the IRB and FDA. For this study, all SAEs or possible UPIRTSOs will be reported to the IRB.

#### **8.5 Medical Monitoring**

It is the responsibility of the Principal Investigator to oversee the safety of the study at his/her site. This safety monitoring will include careful assessment and appropriate reporting of adverse events as noted above, as well as the construction and implementation of a site data and safety-monitoring plan (see section 10 "Study Monitoring, Auditing, and Inspecting"). Medical monitoring will include a regular assessment of the number and type of serious adverse events.

### **9 Data Handling and Record Keeping**

#### **9.1 Confidentiality**

Information about study subjects will be kept confidential and managed according to the requirements of the Health Insurance Portability and Accountability Act of 1996 (HIPAA).

Those regulations require a signed subject authorization informing the subject of the following:

- What protected health information (PHI) will be collected from subjects in this study?
- Who will have access to that information and why?
- Who will use or disclose that information?
- The rights of a research subject to revoke their authorization for use of their PHI.

In the event a subject revokes authorization to collect or use PHI, the investigator, by regulation, retains the ability to use all information collected prior to the revocation of subject authorization. For subjects that have revoked authorization to collect or use PHI, attempts should be made to obtain permission to collect at least vital status (long term survival status that the subject is alive) at the end of their scheduled study period.

## 9.2 Source Documents

Source data is all information, original records of clinical findings, observations, or other activities in a clinical trial necessary for the reconstruction and evaluation of the trial. Source data are contained in source documents. Examples of these original documents, and data records include: hospital records, clinical and office charts, laboratory notes, memoranda, subjects' diaries or evaluation checklists, pharmacy dispensing records, recorded data from automated instruments, copies or transcriptions certified after verification as being accurate and complete, microfiches, photographic negatives, microfilm or magnetic media, x-rays, subject files, and records kept at the pharmacy, at the laboratories, and at medico-technical departments involved in the clinical trial.

